Observational study of the correlation between peripheral Treg cell senescence and serum total cholesterol level

Version: 1.0

Date: December 1st, 2022

Ethics Committee

Tianjin Medical University General hospital

Protocol Abstract

Title	Observational study of the correlation between peripheral Treg cell senescence and serum total cholesterol level
Ethics Committee (Grant Number)	The ethics committee of Tianjin Medical University General Hospital (IRB2022-YX-244-01)
Principal Investigator	[name] (Ph.D.)
Sponsor	Tianjin Medical University General Hospital
Fundings	Natural Science Foundation of China (Grant No. 82071394, 82072166)
Execute Time	12/01/2022-03/31/2023
Recruiting Time	01/01/2023-03/31/2023
Objective	Clarify the correlation between human peripheral Treg cell senescence and serum total cholesterol level
Study Type	Observational
Time Perspective	Cross-Sectional
Enrollment	200 participants
Biospecimen	Description: Whole blood and serum Retention: Samples with DNA
Sampling Method	Probability sample
Condition	Hypercholesterolemia
Inclusion Criteria	1) Age \geq 30 and \leq 60 years old with independent behavior ability. 2) The participants need to fully understand the purpose and content of the study, and voluntarily participate in the study and sign the informed consent.
Exclusion Criteria	1) Pregnant or lactating women. 2) Acute and severe diseases in the last 3 months, including but not limited to, acute myocardial infarction, acute cerebral infarction, cerebral hemorrhage, circulatory failure, respiratory failure (internal diseases), trauma requiring hospitalization, or undergoes surgery under general anesthesia (surgical diseases).

	
3) History of severe diseases, including but not limited to, tumors, serious hematological diseases, serious cardiopulmonary diseases (interventional therapy for coronary artery disease, atrial fibrillation, chronic obstructive pulmonary disease, etc.), renal failure, liver failure, old stroke with serious sequelae.
 
4) Have participated in clinical trials in the past 3 months.
 
5) The investigator considers that not appropriate for inclusion.

Outcome Measures	Treg cell senescence evaluated by the beta-galactosidase (SA-betagal) activity test.
Reference standard	Protocols to detect senescence-associated beta-galactosidase (SA-betagal) activity, a biomarker of senescent cells in culture and in vivo. Nat Protoc 4, 1798-1806, doi:10.1038/nprot.2009.191 (2009)

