Statistical Analysis	All statistical analyses were performed using SPSS Statistics Version 27.0 (IBM, Armonk, NY, USA). A two-tailed p value of less than 0.05 was considered to be statistically significant.

1. Research Background and Objectives

Hypercholesterolemia is a risk factor for the occurrence and development of atherosclerosis. Recent animal studies have found that increased serum cholesterol level is associated with peripheral Treg cell senescence, but clinical evidence is still lacking. The purpose of this study is to analyze the correlation between human peripheral Treg cell senescence and serum total cholesterol level using clinical blood samples, thus laying a foundation for the establishment of novel therapeutic strategies for atherosclerosis based on the regulation of Treg cell senescence.

2. Study design

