2.2 Estimated number of subjects

Estimated by statistical analysis, a total of 200 subjects were randomly selected from the population receiving physical examination in the Cadre Physical examination Center of Tianjin Medical University General Hospital from January 2023 to March 2023.

3. Inclusion, Exclusion and Withdrawal Criteria

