3.3 Withdrawal criteria

1) The subject decides to withdraw from the study.

2) The doctor or the researcher asks the subject to withdraw from the study (e.g. poor compliance).

4. Study procedure

Researchers initiate the study according to the inclusion/exclusion criteria. After confirming the subject has signed the informed consent, doctors will record the past medical history and medication (especially hypolipidemic drugs) in the past 3 months. Thereafter, an additional 6 ml of venous blood will be drawn during the routine blood tests for examinations of Treg cell senescence.

5. Evaluation Parameters

Treg cell senescence will be evaluated by the beta-galactosidase (SA-betagal) activity test.

6. Withdrawal of the subject

The subject has the right to withdraw from this trial at any time for any reason. The researcher should have a thorough understanding and a record of the reasons for withdrawal. Doctors and researchers also have the right to stop the subject from continuing to participate in the trial at any time during the research. Besides, subjects with early withdrawal should not be replaced by others.

As too many subjects withdrawing from the trial will lead to unreliable results, unnecessary withdrawal should be avoided. The falling rate of the trial should be controlled within 20%.

7. Statistical analysis

1. Pearson correlation coefficient was used to evaluate the correlation between the number of Treg cells in peripheral blood and serum total cholesterol level.

2. Taking the serum total cholesterol level of 5.17 mmol/L as the cut-off value, the subjects were divided into normal cholesterol level group and hypercholesterolemia group. Subsequently, the Propensity Score Matching (PSM) method was used to match the subjects according to gender, age and past medical history, and the Student's t-test was performed to compare the difference of Treg cell senescence between the two groups.

3. The serum total cholesterol level was stratified (e.g., trisection or quartering), and the difference of Treg cell senescence among all groups was compared using one-way ANOVA followed by LSD post-hoc test.

8. Trial Management

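### Section 7 item 3 tests ordered cholesterol strata with an omnibus ANOVA that ignores their order, and so loses power against the graded relation the objective asks about

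*Protocol*

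**What the plan says.** The Objective in the Protocol Abstract is to "Clarify the correlation between human peripheral Treg cell senescence and serum total cholesterol level". Section 1 gives the expected direction from animal work, where "increased serum cholesterol level is associated with peripheral Treg cell senescence".

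Section 7 lists three analyses.

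- Item 1: "Pearson correlation coefficient was used to evaluate the correlation between the number of Treg cells in peripheral blood and serum total cholesterol level".
- Item 2 splits subjects at 5.17 mmol/L, matches them by propensity score and compares senescence by t-test.
- Item 3 forms cholesterol strata, with three or four groups given as examples, and states that "the difference of Treg cell senescence among all groups was compared using one-way ANOVA followed by LSD post-hoc test".

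None of the three is named primary. The only decision rule is in the Abstract: "A two-tailed p value of less than 0.05 was considered to be statistically significant". The protocol contains no trend test, polynomial contrast, rank correlation or regression of senescence on cholesterol.

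**The concern.** Tertiles or quartiles of cholesterol have a natural order, and the objective asks whether senescence changes along it. The one-way ANOVA F statistic is the same however the strata are relabelled. It spends two degrees of freedom (three strata) or three (four strata) on every possible pattern of differences, of which a steady gradient is only one. LSD then compares pairs and does not test a gradient either.

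As written, item 3 is the only analysis that looks at senescence over more than two cholesterol levels. If a graded relation exists, the named test will miss it more often than a test on the same strata that uses their order. A significant F also does not by itself show that senescence rises or falls with cholesterol.

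**Working it through.** **Inputs from the protocol.** Two-sided 0.05 (Abstract). N = 200 (Section 2.2: "a total of 200 subjects were randomly selected"). Section 6 allows up to 20% loss without replacement, so as few as 200 × 0.80 = 160 subjects may be evaluable. Three or four strata (Section 7, item 3).

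**The plan's own figure.** Section 2.2 attributes the 200 to a statistical estimate but gives no effect size, standard deviation or power, so it cannot be reproduced. For scale only, the Fisher z formula for a Pearson correlation gives 80% power with 200 subjects at r = tanh((1.960 + 0.842)/√197) = 0.197.

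**Assumptions.** Cholesterol and senescence are bivariate normal with correlation r, and the strata are equal in size. The range r = 0.15 to 0.30 is assumed.

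**Step 1: signal kept by the strata.** With standardised cholesterol, the stratum means are:

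- tertiles: −1.091, 0, 1.091; mean square 2 × 1.091²/3 = 0.793, all of it linear;
- quartiles: −1.271, −0.325, 0.325, 1.271; mean square (1.271² + 0.325²)/2 = 0.861, of which the linear contrast captures 0.856.

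**Step 2: noncentrality.** For the F test, λ = N·r²·s/(1 − r²·s), where s is the mean square above. For the contrast, the numerator uses the linear part and the denominator is unchanged. At N = 200, r = 0.20:

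- tertiles, both tests: 200 × 0.04 × 0.793/(1 − 0.04 × 0.793) = 6.55;
- quartiles, F test: 200 × 0.04 × 0.861/(1 − 0.04 × 0.861) = 7.13;
- quartiles, contrast: 200 × 0.04 × 0.856/0.966 = 7.09.

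The signal is practically the same for both tests. The difference lies in the degrees of freedom over which it is spread.

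**Step 3: power** from the noncentral F distribution, with (k − 1, N − k) df for the ANOVA and (1, N − k) df for the contrast. Each cell gives the F test, then the linear contrast.

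| N | r | Tertiles | Quartiles |
|---|---|---|---|
| 200 | 0.15 | 37.6% vs 47.5% | 34.8% vs 50.5% |
| 200 | 0.20 | 61.8% vs 72.2% | 58.9% vs 75.5% |
| 200 | 0.25 | 82.6% vs 89.5% | 80.9% vs 91.7% |
| 200 | 0.30 | 94.6% vs 97.4% | 94.1% vs 98.2% |
| 160 | 0.20 | 51.6% vs 62.4% | 48.5% vs 65.8% |

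At r = 0.20, 80% power needs 298 subjects for the F test and 242 for the contrast with tertiles (298/242 = 1.23). With quartiles the figures are 310 and 224 (310/224 = 1.38).

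**Step 4: what a significant F shows.** At N = 200, tertile means of 0, 0.5 and 0 SD give a significant F in 85.1% of studies, while the linear contrast stays at 5.0%. Quartile means of 0, 0.5, 0.5 and 0 SD give 84.8% against 5.0%. In simulation of these two patterns (20,000 runs each), a significant F came with an LSD result placing the top stratum above the bottom one in only 2.5% and 2.1% of runs.

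**The case against.** The strongest reply is that the ANOVA is correct for the question item 3 literally asks, namely whether the strata differ, and that its type I error is not in doubt. This stands. The point concerns efficiency and fit to the objective.

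A reader might go further and infer that the plan counts a non-monotone pattern as a positive result. The protocol does not say so. It sets no success rule beyond p < 0.05, and it requires LSD comparisons, which include top against bottom. The simulation in Step 4 shows that these would usually reveal a missing gradient. Nor is there an excess of false positives: with no association, the F test and the contrast each reject 5% of the time.

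The contrast is no proof of monotonicity either. With 50 subjects per stratum and quartile means of 0, 0.6, 0.2 and 0.6 SD, its value is −3(0) − 0.6 + 0.2 + 3(0.6) = 1.4, with standard error √(20/50) = 0.632. That gives z of about 2.2 and about 60% power for a pattern that is not monotone.

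Finally, correlating senescence with continuous cholesterol would be stronger than either test on strata: about 81% power at r = 0.20, N = 200. If such an analysis were planned, an omnibus check across strata would do little harm. It is not in the protocol, because item 1 is written for the number of Treg cells. Item 2 gives a direction for senescence but no gradient.

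**Conclusion.** The point holds as a loss of power and a poor fit to the objective; the planned test is not invalid. Over r = 0.15 to 0.30 at N = 200, the omnibus F gives up about 3 to 10 percentage points with tertiles and 4 to 17 with quartiles. The loss is largest around r = 0.15 to 0.20 and small at r = 0.30.

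These figures rest on an assumed r, an exactly linear relation, normal cholesterol and equal strata. Exact linearity favours the contrast. Item 3 is one of three analyses with none named primary, so the consequence for the study is moderate. The change is worth making because it costs almost nothing and no other planned analysis tests a gradient in senescence.

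**What to change.** In Section 7, item 3, state that the test of association across the ordered cholesterol strata is the one-degree-of-freedom linear contrast, reported with its slope per stratum and 95% CI. Keep the stratum means, the deviation-from-linearity F and the pairwise differences as descriptive checks of shape.

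This takes one sentence, uses an option of the one-way ANOVA procedure in the named software, and needs no further subjects or data. The price is lower power for a purely U-shaped relation, which the deviation-from-linearity F is there to show. The report should also say that a significant contrast does not by itself establish a monotone relation.

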8.1 Ethics

To obtain the approval documents of the clinical trial, researchers should submit the trial protocol and a copy of the research documents including the informed consent to the ethics committee.

The approval documents from the ethics committee should be accompanied by the name list of ethics committee members and their respective responsibilities. These documents will be delivered to the researchers in written form before the start of the study.

Any safety-related issues must be promptly reported to the ethics committee, which includes revision on the trial protocol and modification on the subject information page. The end or early termination of the trial should also be reported.

8.2 Informed consent and data protection agreement

It is the responsibility of the researchers to explain the objectives, study procedures, benefits and potential risks of the trial for each subject. The researchers should receive the informed consent signed by the subject before starting the trial, and keep it properly. The subject should also permit researchers and the clinical trial management agency to check his or her original data. Thus, the reliability of the research findings could be ensured.

The personal information of each subject, including name, gender, age, home address and telephone number, should be collected in detail. And the researcher/doctor should give the subject his or her contact information, so that the subject can contact with him or her when needed. This is also helpful for the research and medical care.

8.3 Subjects privacy

The researchers should protect the privacy of the subject. All research documents can only be identified using the subject's number instead of name or physical examination number. In addition, the grouped table that records the correspondence between the subject's name and number can only be kept by the researcher, and could not be submitted to any institution or individual.

8.4 Modification of the trial protocol

The trial protocol is approved by the ethics committee before starting the trial. During the research, any proposed modification on the trial protocol should be reported to the principal investigator, and then be submitted to the ethics committee for review. The clinical research can only be resumed after the re-approval of the ethics committee.

8.5 Original records certification

Researchers should ensure that the subject's privacy is protected when collecting and organizing data. In addition, the data manager is authorized to review the original records in order to confirm the accuracy of the original data.

8.6 Documents on file

According to relevant laws and regulations, researchers should keep the original records properly for at least 5 years from the end of the study.

8.7 Quality control

The clinical trial management agency has the authority to review the study progress, in order to ensure that the trial is carried out as predetermined and that the research data be veritably recorded.
